### **7.3 Required sample size**

The total number of eyes to be included in the study is **120**. Indeed, based on the statistical calculations and standards described in ISO 11979-7:2018 regarding clinical investigations for ophthalmic implants, intraocular lenses, it is considered that 100 eyes would be sufficient to detect the appearance of any post-operative complications, at a statistically satisfactory rate of probability, and to discriminate the visual acuity results.

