### 2.2 Study design

This is a monocentric, longitudinal, prospective, cohort study for a population of 120 eyes on 60 to 120 patients (depending on mono or bi-lateral surgery conditions) with a cataract, receiving an Lucidis lens implant. After the cataract procedure, data collection will take place during appointments planned by the physician (after one day, one week, one month, six months and one year).

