### 3 SELECTION OF PATIENTS

#### 3.1 Patient selection method

Once the study has been initiated, the investigator will recruit the 60 to 120 patients (120 eyes) in an expected period of 6 months. The inclusion period will end at the inclusion of the last patient.

During this period, the investigator will invite all patients for whom the decision has been made to implant a Lucidis lens to take part in the study, so as to include all patients fulfilling the study inclusion criteria in a consecutive manner.

Prior to inclusion and before carrying out any study-related procedures, the investigator will first inform each patient of the study objectives, the conditions for their participation in the study, and the need to allow the study monitor to have direct access to their medical records. Patients will be given an information leaflet and informed consent form, which they are required to personally date and sign.

Before implanting the Lucidis lenses with any of the following conditions, pre-operative evaluation is performed by the surgeon to consider the potential benefit/risk ratio. In case of contraindications, ie the patient already has pathologies or physiological conditions, which may be aggravated by the lens, or in cases where the lens may interfere with the possibility of examining or treating diseases, the lens will not be implanted and the patient will not be included in the study.

Additionally to exclusion criteria, the risk/benefit ratio is individually assessed for each patient with regards to safety and patient vision performance expectations. Diagnostic, anamnesis, eye biometry combined with way of life and patient expectations are considered prior the selection by the surgeon or proposal to the patient to implant a Lucidis IOL. Lucidis is an EDOF (Extended Depth Of Focus) intraocular lens that provides near and intermediate vision in addition to distance vision. Should a patient's medical status or visual expectations determined as not in adequacy with the device, alternative available devices - such as monofocal or multifocal intraocular lenses would be implanted instead. The choice of the intraocular lens based on the state of the art is an essential parameter evaluated in depth by the physician (through diagnosis, anamnesis, comorbidities, biometry, lenses optical performances, dysphotopsia, patient way of life and expectations, etc.).

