### 7.2 Statistical analysis

The analysis will be comparative and shall concern all patients having agreed to take part in the study. Statistical data will be evaluated for each eye, additionnaly in case of bilateral surgery visual acuity for both eyes will be analysed for each eye and together. The quantitative variables will be described in terms of sample size, mean, standard deviation, median, range and missing data. The qualitative variables will be described in terms of sample size, percentage and missing data. Two-sided 95% confidence intervals will be provided if the endpoint is considered relevant. Wilcoxon and Student significance tests will be used.

An interim statistical analysis will be performed from the 6 months data of all included patients. A final statistical analysis will be performed after the last 1-year follow-up visit of the last patient. Data will be compared to the state of the art data regarding similar lenses available on the market.

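### Sections 7.2 and 7.3: complication rates are to be analysed per eye with optional intervals and no allowance for paired eyes, and the claim that 100 eyes detect any complication is too strong

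*Combined protocol and SAP*

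**What the plan says.** **Sample size.** Section 7.3 sets 120 eyes and adds that "100 eyes would be sufficient to detect the appearance of any post-operative complications, at a statistically satisfactory rate of probability". The basis given is "based on the statistical calculations and standards described in ISO 11979-7:2018 regarding clinical investigations for ophthalmic implants". The section reproduces no complication rate, no numerical probability and no dropout rate, and it does not say what the margin between 100 and 120 is for.

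**Patients and eyes.** Section 2.2 describes "a population of 120 eyes on 60 to 120 patients (depending on mono or bi-lateral surgery conditions"; section 3.1 repeats the range. So 120 eyes may mean anything from 120 single eyes to 60 pairs.

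**Analysis.** Section 7.2 states "Statistical data will be evaluated for each eye". The only both-eyes analysis it adds is for visual acuity. For categorical data, which include complications, "The qualitative variables will be described in terms of sample size, percentage and missing data". On precision, "Two-sided 95% confidence intervals will be provided if the endpoint is considered relevant"; neither the relevant endpoints nor an interval method is named. Finally, "Data will be compared to the state of the art data regarding similar lenses available on the market".

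**Objective.** Section 1.2 includes listing surgical complications and adverse reactions among the aims, and makes adverse reactions a secondary objective.

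**The concern.** There are two linked problems.

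First, when both eyes of a patient are operated, a complication in one eye is likely to be informative about the other. An interval that counts the eyes as independent then claims more information than the study has. The effect is easiest to see at zero cases, a plausible result for a rare complication in a study of this size. As written, 7.2 leaves open whether such a complication appears as 0% with no upper limit, or with a limit that ignores pairing. It also leaves the choice of which endpoints get an interval until after the results are known. Since the results are to be set against published data on similar lenses, either presentation could make the safety findings look firmer than they are.

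Second, 7.3 tells the reader that 100 eyes are enough for any complication. No finite sample can do that. Without a rate and a probability, the reader cannot tell what a blank line in the complication table excludes.

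**Working it through.** **Inputs from the documents.** 120 eyes in 60 to 120 patients (2.2, 3.1); 100 eyes said to suffice (7.3); two-sided 95% intervals (7.2).

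**Assumptions.** Detection probability 95%; between-eye correlation r from 0.25 to 0.75, with r = 0 and r = 1 as the ends; and, for the mixed example, 30 pairs plus 60 single eyes (120 eyes, 90 patients). The documents give no correlation and no bilateral share.

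**Step 1: the 100-eye figure.** It cannot be reproduced from 7.3, because both the rate p and the probability P are missing. What can be checked is which inputs would fit. For n independent eyes, P(at least one case) = 1 − (1 − p)^n.

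- Eyes needed to see a 3% complication at least once with 95% probability: ln(0.05)/ln(0.97) = 98.4, so 99. A figure of 100 is consistent with this.
- Smallest rate seen at least once with 95% probability, 1 − 0.05^(1/n): 2.95% with 100 eyes, 2.47% with 120. With 60 fully concordant pairs, n = 60 gives 4.87%.
- Chance of missing a 1% complication: 0.99^100 = 36.6%; 0.99^120 = 29.9%. Seeing it with 95% probability takes 299 eyes.

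**Step 2: per-eye limit at zero cases, eyes independent.** The exact two-sided 95% upper limit is 1 − 0.025^(1/120) = 3.03%.

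**Step 3: the same limit allowing for pairing.** For a pair with per-eye rate p and correlation r, P(neither eye affected) = (1 − p)² + r·p(1 − p) = (1 − p)(1 − (1 − r)p). With a pairs and b single eyes, the upper limit solves

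[(1 − p)(1 − (1 − r)p)]^a × (1 − p)^b = 0.025.

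The last two columns put p = 3.03% into the left-hand side. They give the chance of seeing no case when the true rate equals the independent-eyes limit, which should be 2.5%.

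| r | Upper limit, 60 pairs | Upper limit, 30 pairs + 60 single | P(no case), 60 pairs | P(no case), 30 pairs + 60 single |
|---|---|---|---|---|
| 0 | 3.03% | 3.03% | 2.50% | 2.50% |
| 0.25 | 3.46% | 3.23% | 3.99% | 3.16% |
| 0.75 | 4.82% | 3.72% | 10.02% | 5.01% |
| 1 | 5.96% | 4.02% | 15.81% | 6.29% |

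**Step 4: patient-level limit at zero cases.** The Clopper-Pearson upper limit for 0 of N patients is 1 − 0.025^(1/N): 3.03% for N = 120, 4.02% for N = 90, 5.96% for N = 60. These equal the r = 1 values in Step 3. A patient's chance of at least one affected eye cannot be lower than the per-eye rate. At zero cases the patient-level limit is therefore also a conservative bound on the per-eye rate, with no correlation assumed.

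**The case against.** **The 3.0% and 6.0% limits are not a like-for-like comparison.** A reader might infer that the plan understates the upper limit by half, since 0 of 120 eyes gives 3.0% and 0 of 60 patients gives 6.0%. That does not follow. The first is a per-eye rate and the second is the proportion of patients with at least one affected eye. With 60 pairs of fully independent eyes, a per-eye rate of 3.03% already gives 1 − (1 − 0.0303)² = 5.96% per patient, so the gap appears even without correlation. The effect of pairing is the per-eye shift in Step 3. This objection stands in full.

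**The standard may hold the inputs.** Section 7.3 cites an ISO standard that may state a rate and a probability, and 100 eyes do fit about 3% at 95%. A reader might infer a calculation error; the documents do not support that. The wording could also be read as seeing whether complications occur at all. What remains is that the protocol does not state the inputs and that its unqualified wording promises too much.

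**A patient-level rate is awkward to compare.** It mixes patients with one and two operated eyes and depends on the bilateral share. This is true, so it should stand beside the per-eye percentage and not replace it.

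**Every complication is not a defined set.** The list of 26 reactions in section 1.3 is expressly not exhaustive, and sections 4.5 and 4.6 foresee losses to follow-up. A list and a denominator are needed, and the fix includes both.

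**The study is observational and descriptive.** No test or stopping rule uses complication rates, and 7.2 permits intervals. That limits the consequence, but in a descriptive safety study the estimate and its precision are the result. The documents do not say that zero cases will be shown without a limit; they only leave it open.

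**Conclusion.** The concern holds. Section 7.2 neither guarantees an interval for complications nor allows for paired eyes. At zero cases a per-eye limit that ignores pairing would read 3.0%. At assumed correlations of 0.25 to 0.75 it should read 3.5% to 4.8% if all patients are bilateral, or about 3.2% to 3.7% with 30 pairs plus 60 single eyes. Full concordance gives 6.0% and 4.0%. If all patients have one operated eye, there is no error. The size therefore depends on a correlation and a bilateral share that the documents do not give, and the figures take all 120 eyes as followed.

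Section 7.3 overstates what 100 eyes can show. At an assumed 95% probability the threshold is about 3% per eye with independent eyes, and a 1% complication is missed 37% of the time (30% with 120 eyes). This part is mainly a matter of stating inputs and moderating the wording. Neither problem invalidates the study, but both should be corrected before the six-month interim analysis.

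**What to change.** **Section 7.2.**

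- Pre-specify a list of complications, for example the reactions in section 1.3, and add any other complication observed.
- For each, including those with zero cases, report an exact two-sided 95% Clopper-Pearson interval on the proportion of followed patients with at least one affected eye, labelled as patient-level.
- Show the per-eye percentage beside it, with the numbers of unilateral and bilateral patients.
- Require that any per-eye interval allows for pairing. At zero cases, where a cluster-robust standard error is zero or cannot be estimated, use the patient-level upper limit as a conservative bound on the per-eye rate.

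**Section 7.3.** Replace the claim about any complication with the rate observable at least once at a stated probability, which the sponsor confirms against the cited standard. If that probability is 95%, the text could read: about 2.5% per eye with 120 independent eyes, 3.0% with 100, and up to 4.9% with 60 fully concordant pairs; observing no case does not exclude rates up to the upper limit reported under 7.2. Do not describe 100 as the evaluable number unless the sponsor confirms it.

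**Cost.** New wording in two sections, a list, a rule for the follow-up denominator and extra columns in the complication table. No more patients, visits or measurements are needed: forms are completed per eye and patients carry an identification number (7.1), and uni- or bilateral status is recorded at inclusion (4.3.1). The price is wider intervals, a less favourable statement of detection ability, and a patient-level rate that mixes patients with one and two operated eyes.

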## 8 ETHICAL AND LEGAL CONSIDERATIONS

### 8.1 Medical-regulatory framework of the study

The procedures described in this protocol, concerning the implementation, evaluation and documentation of the study are designed to ensure that the sponsor and investigating physician comply with the ethical principles defined in the Declaration of Helsinki and with the Good Clinical Practice according to the standard ISO 14155: 2011.

The study will be conducted in compliance with Swiss Law and Swiss regulatory authority's requirements and European regulatory requirements and legislation.

This observational study does not require additional biological samples of any type whatsoever, other than those normally prescribed by the physician. Except for 2 additional follow-up visits (month 6 and Year 1) and additional examination under mesopic conditions, it does not change the way in which the physician manages the patient.

### 8.2 Investigator's responsibilities

The investigator is responsible for ensuring that the study is conducted in accordance with Good Clinical Practice (GCP) guidelines as well as all the regulations governing the conduct of clinical trials in Switzerland.

Good Clinical Practice (GCP) guidelines aim to protect the rights, safety and welfare of persons taking part in research, together with the credibility and confidentiality of personal data and the study results. GCP are international standards of ethical and scientific quality concerning the development, conduct, recording and reporting of studies involving human participants.

Compliance with these reference standards provides assurance that the rights, safety, protection and well-being of patients in the study will be respected in accordance with the principles laid down in the Declaration of Helsinki, and that the clinical study data are reliable (genuine, precise and accurate).

### 8.3 Ethics committee

The present protocol was drawn up based on the generic standard ISO 14155:2011 (Clinical investigation of medical devices for human subjects. Good clinical practice).

EU Regulation 2017/745, concerning medical devices was taken into account, together with the Federal Act on medicinal products and medical devices (Act on therapeutic products) and the ordinance on clinical trials on therapeutic products.

This study can only be undertaken after approval of the protocol and appendices has been obtained from the relevant Ethics Committee. During the study, the following documents must be submitted to the Ethics Committee for review:

- Any amendments to the protocol
- Any changes to the information leaflet and informed consent form or any document to be given to the patient.
- All cases of SAEs related to the lens implant
- new investigator notification
- any new information concerning the safety of the device or which may interfere with the conduct of the study
- protocol deviations which may affect the results of the study.

During the study, amendments to the protocol which alter the risks and obligations of the patients, amendments and revisions made to the information leaflet and informed consent form, together with any substantial amendments must be promptly submitted to the Ethics Committee for review and approval prior to implementing any such changes.

At the end of the study, the sponsor shall notify the Ethics Committee of the end of the study, then send it the safety report, together with a summary of the study report.

#### **8.4 Patient information leaflet and informed consent form**

Each patient must give his/her written informed consent after receiving a full explanation about the nature of the study. The consent form (the content of which has been approved by the Ethics Committee) must be dated and signed prior to the execution of any study-related procedures.

Before enrolment in the study, the investigator must explain the nature of the study and the consequences of their participation to the selected patients. Patients must be informed about the voluntary nature of their participation and their right to withdraw their consent at any time without affecting the quality of their future care in any way. They will be informed that alternative treatments are available should they refuse to take part in the study. Finally, they must be informed that the competent authorities and sponsor's representatives may have access to their personal study data, but that the confidentiality of this information will be respected according to current laws and regulations. The patient must be given sufficient time to read the informed consent form and to ask further questions.

After signature, a copy of the information leaflet and informed consent form will be given to the patient and a copy will be kept by the investigator on the investigation site.

The participation to the study will not generate additional cost to the patient or their health insurance. The sponsor will reimburse the additional visits based on proof of invoice for the following eligible costs:

- Outward and return trip from the place of residence to the investigator
  - Car: 70cts / km
  - Train: actual cost in second class
  - Taxis: Actual costs up to a maximum of CHF 50 per trip
  - Medicalized car: costs not covered by health insurance reimbursed
  - Ambulance / not reasonably mobile: not reimbursed and/or withdrawal from the study

The cost refund by the sponsor will be made through the investigation center, the investigation center will provide the refund directly to the patient as the sponsor must not have access to patient's personal data.

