# Evaluation of efficacy and long-term safety for Lucidis Instant Focus© - PMCF Study protocol

Version 9 - Page 14/25

SWISS ADVANCED VISION

INTRAOCULAR LENS

Collected data	Screening (study inclusion)	Baseline visit (D - 14-1)	Surgical procedure (D)	Follow-up Day 1 (D1-2)	Follow-up Week 1 (D7-10) Follow-up Month 1 (D30-45) Follow-up Month 6 (D180-195)  Follow-up Year 1 (D360-390) 
Informed consent	X				
Demographics	X				
Inclusion / exclusion criteria	X				
Candidate eye(s) for operation	X				
Slit lamp examination		X		X 	X
Cataract history		X			
Contrast sensitivity Photopic (85–100 lx) and Mesopic (3 lx)		X		X 	X
Uncorrected Visual Acuity – Far Photopic (85–100 lx) and Mesopic (3 lx)		X		X 	X
Uncorrected Visual Acuity – Intermediate Photopic (85–100 lx) and Mesopic (3 lx)		X		X 	X
Uncorrected Visual Acuity – Near Photopic (85–100 lx) and Mesopic (3 lx)		X		X 	X
Best Corrected Visual Acuity - Far		X		X 	X
Defocus curve* Photopic (85–100 lx) and Mesopic (3 lx)		X		X 	X
Abberometry		X		X 	X
Operated eye			X		
Lens information			X		
General surgical procedure information			X		
Adverse event during surgery			X		
Adverse event spontaneously reported by patient				X	X
Specific interview: visual acuity, frequency of glare and halo, distorted vision				X	X
Change in medication intake				X	X

\*only for the first 40 patients. In case of patient withdrawal, data will be collected on a new patient to obtain data on a minimum 40 patients, whenever possible.

X: at the discretion of the investigator

: Additional follow up visits compared to standard procedure

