#### **4.6 End of study - withdrawal from the study**

The patients will be considered to have completed the study after they have undergone a final evaluation 1 year after the inclusion visit.

The following may be considered to have withdrawn from the study:

- Patients who have requested to do so (verbal or written) via the investigator;
- patients lost to follow-up by the center, unable to be reached;
- Included patients presenting an exclusion criterion during the study (for example, inclusion in an interventional therapeutic trial).

In case of withdrawal of informed consent, non-compliance, disease progression, safety, etc. the study procedures might be stopped but the routine follow-up should be performed due to safety concerns. Data previously obtained will be retained and analyzed.

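### A travel-cost line in section 8.4 permits withdrawal of patients who cannot readily travel to Month 6 and Year 1, a ground section 4.6 does not list, so some late data may be lost selectively

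*Combined protocol and SAP*

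**What the plan says.** Section 8.4 introduces its travel-cost list with "The sponsor will reimburse the additional visits based on proof of invoice for the following eligible costs". Car, train and taxi travel are reimbursed at stated rates or up to a limit. For a medicalized car, the sponsor pays what health insurance does not. The last line reads "Ambulance / not reasonably mobile: not reimbursed and/or withdrawal from the study". The same section also promises: "The participation to the study will not generate additional cost to the patient or their health insurance".

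The additional visits are identified in two places. Section 8.1 says the study leaves patient management unchanged with this exception: "Except for 2 additional follow-up visits (month 6 and Year 1) and additional examination under mesopic conditions". The schedule table in section 4.4 marks the same two visits with the footnote "Additional follow up visits compared to standard procedure".

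Section 4.6 opens its list of withdrawals with "The following may be considered to have withdrawn from the study" and names three cases: the patient's own request, loss to follow-up, and an exclusion criterion that arises during the study. It then says that in cases such as withdrawn consent, non-compliance or safety, "the study procedures might be stopped but the routine follow-up should be performed due to safety concerns". It closes with "Data previously obtained will be retained and analyzed".

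**The concern.** A ground for leaving the study appears in a list of travel costs and not in the section that governs withdrawal. It bears on the two visits that supply the 6-month interim analysis, the 1-year final analysis and most of the evidence for the long-term safety aim in section 1.2.

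Loss of mobility during the year is unlikely to be random. It may follow an illness, a fall or a hospital stay. Section 6.1.1 counts lasting disability and inpatient hospitalisation among the criteria for a serious adverse event, so some of these patients may meet the protocol's own definition. If they are withdrawn, the reason their later data are missing may be tied to the outcomes under study. Section 7.2 plans only to describe missing data. It has no sensitivity analysis and no breakdown by reason for withdrawal.

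**Working it through.** **1. Which visits are affected.** The cost list in 8.4 applies to the additional visits. Section 8.1 and the table footnote in 4.4 both identify these as Month 6 and Year 1.

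**2. Whether 4.6 covers the gap.** Its list does not name mobility. It asks for routine follow-up after study procedures stop, but Month 6 and Year 1 lie outside standard procedure, so routine follow-up does not supply them. Section 6.2.2 collects non-serious events only up to the last study procedure. A patient withdrawn after Month 1 therefore has no planned Month 6 or Year 1 event or acuity data. A patient withdrawn after Month 6 loses only Year 1.

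**3. What is kept.** Data obtained before withdrawal are retained (4.6). Hospitalisations, with listed exceptions, are reportable (6.1.1). Serious events are reported within 24 hours of notification and followed beyond study end if unresolved (6.2.1). Non-serious events are recorded from consent, whatever their cause (6.2.2). An event that causes the immobility comes before the withdrawal and should already be in the data.

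**4. The plan's own number.** Section 7.3 includes 120 eyes and calls 100 sufficient, without giving an event rate, power or dropout rate, so the 120 cannot be reproduced. The gap is 120 − 100 = 20 eyes, or 20/120 = 16.7%. The plan does not call it a dropout allowance. It protects the number of eyes, not their representativeness.

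**5. Illustrative size, event rates.** All inputs here are assumptions: f is the share of eyes withdrawn for immobility, p the late event rate in the others, and k the risk ratio. If withdrawn eyes drop out of numerator and denominator:

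- true rate = (1 − f)p + f·k·p; observed rate = p
- relative understatement = 1 − 1/[1 + f(k − 1)]

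| f | k = 2 | k = 3 |
|---|---|---|
| 2% | 2.0% | 3.8% |
| 5% | 4.8% | 9.1% |
| 10% | 9.1% | 16.7% |
| 15% | 13.0% | 23.1% |

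In absolute terms with p = 5% and k = 3 to 5:

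- f = 5%: 0.95 × 5% + 0.05 × 15% = 5.5%, and 0.95 × 5% + 0.05 × 25% = 6.0%
- f = 10%: 0.90 × 5% + 0.10 × 15% = 6.0%, and 0.90 × 5% + 0.10 × 25% = 7.0%

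The shift from the observed 5.0% is thus 0.5 to 2.0 percentage points. For comparison, 6 events in 120 eyes (5.0%) have an exact 95% interval of 1.9% to 10.6%, treating eyes as independent.

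This formula treats every event in the withdrawn group as unseen. For a cumulative rate with everyone kept in the denominator, if a share s of that group's events falls before withdrawal and is retained, the shortfall is (1 − s)·f·k·p. That is smaller than the f(k − 1)p used above whenever s exceeds 1/k, for example one third at k = 3. The documents give no timing of events.

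**6. Illustrative size, acuity.** If the missing eyes are on average d worse, the mean looks better by f·d. With d = 0.1 to 0.2 logMAR (assumed), this is 0.005 to 0.010 logMAR at f = 5% and 0.010 to 0.020 at f = 10%.

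**The case against.** A reader might infer that the rule removes the frailest patients, that their serious events go uncollected, and that Year 1 results will therefore look too good. The documents do not support that.

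- **Withdrawal is optional.** The line can be applied as non-reimbursement alone.
- **The group is narrow.** A patient with reduced mobility who can use a medicalized car is reimbursed for what insurance does not cover. Section 3.3 already keeps out patients unable to comply with follow-up. What remains is mainly severe immobility that develops later. Poor vision alone does not place a patient in this group.
- **Earlier events stay in.** As step 3 of the working shows, the event that causes the immobility should be reported and retained.
- **Section 4.6 need not be read as exhaustive.** Its list is worded permissively, and the paragraph after it ends its examples with an open et cetera. It also allows study procedures to stop while routine follow-up continues, so 8.4 does not directly contradict its safety intent.
- **The size is assumed throughout,** and the illustrated shifts lie well inside sampling error.

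All of this stands as a limit on size and certainty. It does not remove the gap: later events and acuity at one or two visits can be lost under a stated rule, and routine follow-up does not replace those visits. A shift inside the confidence interval is still a bias, and the interval does not reflect it. That these patients have worse outcomes is a reasonable inference, not something the documents state.

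**Conclusion.** The point holds as a modest one. Section 8.4 permits a form of withdrawal that 4.6 does not list, at the two visits that carry the long-term results. If it is used, late events and acuity may be missing selectively, and late results may look somewhat better than they are. The direction rests on the inference that patients who become immobile do worse. The size cannot be derived from the documents and is probably small unless several per cent of eyes are affected.

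A separate inconsistency sits within 8.4. Refusing to reimburse transport to a visit the sponsor has added does not fit the promise of no additional cost to the patient, and could cause missed visits even if no one is withdrawn.

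**What to change.** - **Section 8.4:** delete the withdrawal option from the ambulance line and reconcile the section with 4.6.
- **Sections 4.5 and 4.6:** state that a patient who cannot travel stays in the study unless they withdraw consent. The missed visit is documented and justified as 4.4 already requires. Adverse events and complications are obtained by telephone or from the treating ophthalmologist within the Month 6 and Year 1 windows. Only acuity that could not be measured is recorded as missing, with the reason.
- **Section 7.2:** report withdrawals and missed visits by reason.
- **Section 8.4, costs:** reconcile the refusal to reimburse with the no-additional-cost statement. Otherwise patients kept in the study could face uncovered transport costs.

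The cost is a protocol amendment, and any matching change to the patient leaflet, submitted to the Ethics Committee under 8.3, plus a few telephone contacts. The change is best made before follow-up begins, because events not collected at the time may not be recoverable later.
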